**1. OVERALL SYNOPSIS OF THE CLINICAL INVESTIGATION**

Clinical investigation title:	Form, Fit, and Function of INVSENSOR00061
Study objective(s):	The objective of this study is to evaluate the form, fit, and function of INVSENSOR00061 in generally healthy subjects ages 0-18 months.
Investigational device(s):	Masimo INVSENSOR00061
Number of subjects:	Approximately 25 subjects
Inclusion criteria:	Refer to section 6.3.1.
Exclusion criteria:	Refer to section 6.3.2.
Duration of the clinical investigation:	The expected duration of study enrollment is 1 to 3 months. The expected duration of each subject's participation in the lab will be approximately 120 minutes (2 hours). Subject may participate in home studies with an expected duration of approximately 2 days (48 hours).
Study endpoint(s):	Evaluate the form, fit, and function of INVSENSOR00061

**2. IDENTIFICATION AND DESCRIPTION OF THE INVESTIGATIONAL DEVICE**

Masimo Corporation and Cercacor develop noninvasive medical technologies. These devices may have applications in a home setting, the operating room, critical care unit, emergency room, emergency transport vehicles, alternative (home) care, as well as physician's offices.

**2.1. FDA Cleared/Consumer Noninvasive Sensors and Devices**Masimo Patient Monitoring Platform (Root® or comparable)

Root is a patient monitoring and connectivity platform that offers rainbow® and Masimo SET® measurements with other parameters in an integrated platform. With docking capabilities for the Radical-7® handheld monitor and Radius-7™ patient-worn monitor and multiple networking/connectivity options, Root integrates multiple streams of data into one display monitor.

Pulse Oximeter Sensors and Cables (Masimo SET®, Masimo rainbow®, or comparable)

Masimo rainbow and SET noninvasive pulse oximeter sensors vary in LEDs and parameters enabled in the sensor. Masimo pulse oximeters may also differ in intended care areas such as spot check or continuous measurements, design of sensor application such as finger clips or adhesive, and patient population such as adults, neonates and pediatrics.

**2.2. Investigational Devices**Masimo INVSENSOR00061

INVSENSOR00061 is designed to provide parents with access to hospital-grade, clinically proven vitals monitoring technologies, such as Masimo SET®, at home. INVSENSOR00061 offers continuous monitoring of blood oxygen level (SpO2), pulse rate (PR), [REDACTED]. INVSENSOR00061 is inserted into a bootie holder so that it can be held in place on the subject's foot. The bootie holder which is made from a soft silicone material with fabric straps, [REDACTED].

## 2.3. Site Information

The Masimo Clinical Laboratory facility is designed as a Phase 1 clinical study research center. The laboratory is staffed by physicians, anesthesiologists, certified registered nurse anesthetists, registered nurses, medical assistants, and clinical research staff. All personnel undergo routine required training on GCP and human research subject protections. The laboratory is equipped with standard FDA-approved medical monitoring equipment including ECG monitors, blood pressure monitors, pulse oximeters, standard hematology analyzers, and has emergency crash carts available. Hospitals and urgent care facilities are within three miles of the Masimo Clinical Laboratory.

## 3. JUSTIFICATION FOR THE DESIGN OF THE CLINICAL INVESTIGATION

Pulse oximetry is commonly used as a standard of care (SOC) in critically ill patients in intensive care units and used in surgical operations to monitor oxygen saturation (SaO2) levels. The advantage of this noninvasive technology is that it allows for the detection of hypoxia [1].

Oxygen saturation levels represent the ratio between oxyhemoglobin (oxygenated) and deoxyhemoglobin (non-oxygenated) present in the blood [2]. The pulse oximeter works by measuring frequencies of light, which correspond to the type of hemoglobin present in the blood. By isolating the pulsatile signal, the oxygen saturation of arterial hemoglobin can be estimated.

Masimo Corporation develops noninvasive medical technologies such as Masimo Signal Extraction Technology (SET®), which is incorporated in Masimo SET® pulse oximeters and adhesive sensors. Masimo SET® signal processing is designed to overcome limitations of conventional pulse oximetry technologies distinguishing between pulsating blood in arterial and venous blood at the measurement site. Masimo SET® pulse oximeters have been FDA-cleared for the monitoring of SpO2, PR, and RRp in motion and non-motion conditions. Studies have found fewer false alarms and more accurate true alarm detection. Masimo SET® pulse oximeters use advanced signal processing algorithms to filter out noise, such as moving venous signals, to help improve the detection of the true arterial oxygen saturation [3].

The objective of this study is to evaluate the form, fit, and function of INVSENSOR00061 when used on newborn and infant subjects. To evaluate the form, fit, and function, the study will look to collect data on the application, fit, and ability to obtain the supported parameters on the intended study population. To confirm the acceptability of the form, fit, and function for each subject a standard of care FDA cleared adhesive sensor will be applied to each subject as a reference. The standard of care sensor is provided as reference in the study because it is possible that a very small population of subjects may have physiologies that may make the supported parameters difficult to obtain.

## 4. BENEFITS AND RISKS OF THE INVESTIGATIONAL DEVICE, CLINICAL PROCEDURE, AND CLINICAL INVESTIGATION

### 4.1. Anticipated Benefits

There would be no medical benefits to the subject. Other possible benefits would be to society as a whole. Development of new technology could enable healthcare workers to more appropriately recognize and treat potentially life-threatening conditions.

### 4.2. Risks/Discomforts Associated with Participation in the Clinical Investigation

The studies will be conducted per IRB-approved procedures. The study subjects will consist entirely of generally healthy volunteers. The readings obtained during the study will be recorded, but will not be used in patient care, monitoring, or diagnosis.

- Risks Associated with the Device

The noninvasive devices used in this study are similar in technology and design to some commercially

available pulse oximeters and other noninvasive devices and hence have the same risks. Pulse oximeters and other noninvasive devices are commonly used and are considered to be minimal risk.

There is a small risk of damage to the subject's foot, from the device, including temporary skin irritation, skin inflammation, itching skin, or discomfort associated with exposure to the sensor, as well as potential temporary mechanical irritation or discomfort.

There is a remote, yet possible, risk of a burn from the sensor. In the case of a sensor burn, there is the potential for permanent skin damage (scar/discoloration).

If there are any cuts and/or abrasions near the foot, sensors may not be placed on the particular foot to avoid any discomfort for the subject.

- **Risks Associated with Skin Preparation**

Subjects may be asked to use an alcohol pad or comparable on the area of sensor application to allow the sensors to adhere to the skin. Risks associated with the skin preparation include rash, flushing or redness of the skin, unusually warm skin, skin inflammation, and/or skin irritation. Each of these discomforts and side effects are temporary and should fade over time.

If there are any cuts and/or abrasions near the area of sensor application, certain types of skin preparation materials may not be used on the particular location to avoid any discomfort for the subject.

- **Risks from Inflicted Knowledge**

The risk of inflicted medical knowledge to subjects is negligible since we de-identify all associated information including those relevant to our clinical and engineering parameter studies. The monitoring and test results are not examined for diagnostic purposes and do not reflect an attempt to ascertain any subject's medical condition. The attending physician's role during this study is to ensure the safety of the subject during the study.

We will reduce the risk of inflicted knowledge by assuring the subject's parent(s) that the device readings are for research use only. In the case that the subject's parent(s) become aware of a condition (hypertension, arrhythmia, etc.) they have during the course of our study, our study staff will recommend that they contact their primary care physician and we will document this recommendation. As part of that process, we will follow up with these individuals prior to enrollment if their condition meets exclusion criteria for a study.

- **Risks from Loss of Confidentiality**

Masimo upholds the highest standards to protect hard and electronic data, however, a complete promise for confidentiality cannot be guaranteed due to unforeseeable events.

### 4.3. Emergency Response Plan for Medical Emergencies

A crash cart equipped with medications to provide immediate care during emergencies is on site and full emergency services are within 3 miles.

Study staff will dial 911 for medical emergencies that require emergency medical services (EMS) to be contacted.

### 4.4. Alternatives

The alternative is to not participate in the study.

### 5. OBJECTIVES OF THE CLINICAL INVESTIGATION

The objective of this study is to evaluate the form, fit, and function of INVSENSOR00061 in generally healthy subjects ages 0-18 months.

### 6. DESIGN OF THE CLINICAL INVESTIGATION

#### 6.1. General

##### 6.1.1. Clinical Investigation Design

This is a nonrandomized single arm study wherein all subjects are enrolled into the experimental arm and have Masimo INVSENSOR00061 placed on their foot.

##### 6.1.2. Measures Taken to Minimize/Avoid Bias

Subjects are selected from the population surrounding the test site [REDACTED]

Where applicable, subjects with required demographics (skin pigmentation, race/ethnicity, age, gender, etc.) may be preferentially recruited.

##### 6.1.3. Equipment and Materials

Equipment and materials are to be used as required. All lab equipment will be maintained per manufacturer specifications and all study personnel will be trained in the use of relevant equipment.

###### Safety Equipment (FDA-Cleared)

- Masimo Patient Monitoring Platform (Root® or comparable)
- Masimo Pulse Oximeters (Radical-7®, Rad-97™, Radius-7®, or comparable)
- Pulse Oximeter Sensors and Cables (Masimo SET, Masimo rainbow, or comparable)
- Medical-grade oxygen tank and mask
- Blood pressure monitoring system
- Electrocardiogram (ECG)
- Crash cart

###### Test Devices (FDA-cleared, consumer products, or investigational)

- Masimo INVSENSOR00061
- FDA-cleared pulse oximeter

###### Research Equipment

- [REDACTED]
- [REDACTED]
- [REDACTED]

##### 6.1.4. Standard Safety Precautions

Any emergency drug deliveries in the case that a subject loses consciousness or has another emergency arise shall be recorded. This individual will be monitored, and this information will be recorded and submitted to the IRB if necessary, as outlined in section 14.3. The subject will be given the option to follow up with a local urgent care facility.

The subject will be monitored through observation by clinical study staff throughout the study procedure.

An additional pulse oximeter may occasionally be used for the duration of the study to monitor subjects' vital parameters to ensure their safety.

All adverse events will be recorded.

The subject's parent(s) will be informed of the type of procedure that they will be participating in before enrollment in the study.

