#### 6.4.1.2. Phone Screening

Once the potential subject's parent(s) or legal guardian see the recruitment material (e.g., advertisement), they can contact us to inquire more details about the study. The recruitment process is managed by the designated person(s) who is trained for phone screening/scheduling.

Virtual or In-person appointments are made once the phone screening process is completed and the person screening the subject determines if they qualify for the study based on inclusion/exclusion criteria.

Information from the screening will be kept in a database located within the firewall-protected Masimo internal network with user level access control enforced domain log in. Additionally, the database is encrypted and password protected. The information is kept to contact the subject's parent(s) for other studies they may qualify for or for instance, to track subjects who call in and provide false information only to qualify.

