### 6.4.4. In-Person Sensor Placement Procedure and Data Collection

Prior to the placement of INVSENSOR00061, the subject may be observed for crying, restlessness, etc. If applicable, the observations will be recorded on the subject's CRF.

The area of sensor application may be prepped using an alcohol pad or comparable. INVSENSOR00061 will be placed on the opposite foot of the FDA-cleared sensor.

An FDA-cleared sensor will be placed on the subject's foot, depending on subject's weight, following manufacturer's DFU and the study's procedure manual. Continuous data from the pulse oximeter will be collected.

INVSENSOR00061 will be paired via Bluetooth connection to data collection software on a laptop or a phone. Upon successful Bluetooth pairing of the investigational device, data collection will be initiated on the data collection software and data will be obtained continuously (SpO2, PR, [REDACTED]).

Data will be collected for approximately 90 minutes using the data collection software. The subject may be observed for crying, restlessness, etc. If applicable, the observations will be recorded on the subject's CRF.

Standard of care and the study sensor placement locations, study sensor ID/lot number, the subject's reaction prior to and after sensors placement, observations during data collection, and other relevant information will be recorded in the CRF.

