### 6.4.5. Virtual Sensor Placement Procedure and Data Collection

The subject's parent(s) or legal guardian may be asked to prep the area of sensor application using an alcohol pad or comparable which will be provided. INVSENSOR00061 may be placed on the opposite foot of the FDA-cleared sensor.

An FDA-cleared sensor may be placed on the subject's foot, depending on subject's weight, following manufacturer's DFU. Continuous data from the pulse oximeter will be collected via Bluetooth.

INVSENSOR00061 will be paired via Bluetooth connection to data collection software on a laptop or a phone. Upon successful Bluetooth pairing of the investigational device, data collection will be initiated on the data collection software and data will be obtained continuously (SpO2, PR, [REDACTED]).

Data may be collected overnight while the subject is asleep for up to two days using the data collection software. The subject may be observed for crying, restlessness, etc. If applicable, the observations will be recorded in the data collection device.

Standard of care and the study sensor placement locations, study sensor ID/lot number, the subject's reaction prior to and after sensors placement, observations during data collection, and other relevant information may be recorded in data collection device.

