## 8. DATA MANAGEMENT

### 8.1. Data Management and Confidentiality

All documents associated with this protocol will be securely stored in a physical location or on password-protected computers. The confidentiality and retention of these documents will be protected to the extent provided and required by the law. All data will be de-identified before any statistical analysis. Only de-identified data will be shared with Masimo for research purposes stated in this protocol. Data collected by data capture software and data entered in case report form will be shared with Masimo via a secure, password-protected server that only study staff and Masimo study team members will have access to. Data will be retained for a minimum to 2 years following completion of the final analysis.

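### Section 6.1.4 promises staff observation without limit, but 6.4.5 describes home collection with no staff observation and only an optional record of the infant's reaction

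*Combined protocol and SAP*

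**What the plan says.** Section 6.1.4 falls under 6.1 General, ahead of both the in-person and the virtual procedures. It reads: "The subject will be monitored through observation by clinical study staff throughout the study procedure." It also requires every adverse event to be recorded.

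Section 6.4.5 covers the virtual route: "Data may be collected overnight while the subject is asleep for up to two days using the data collection software." It makes observation of the infant optional and names no observer. On recording, it says that the subject's "reaction prior to and after sensors placement, observations during data collection, and other relevant information may be recorded in data collection device." The matching sentence for the lab, in 6.4.4, says that the subject's "reaction prior to and after sensors placement, observations during data collection, and other relevant information will be recorded in the CRF."

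Section 4.2 lists skin irritation, inflammation, itching and discomfort, and a remote risk of a burn. Section 4.3 places a crash cart at the site. Section 14.3 requires all adverse events in the CRF and the Adverse Event Report Form. It allows 48 hours for reporting serious adverse events and unanticipated adverse device effects to the sponsor, and 5 business days for other events. Section 8.3 reserves CRF entries for authorized site staff. Section 6.4.6, the ending procedure, covers removal and return of the devices, by mail or drop-off, and asks for no record of the skin.

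**The concern.** A home session run as 6.4.5 describes does not meet 6.1.4 as written. Site staff, the monitor and the IRB cannot tell from the protocol whether the observation commitment covers home use.

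The second issue is the completeness of the data. The record of how the infant reacted is required where staff are present and optional where none are described. Section 3 says that the study will collect data on application and fit, so this record bears on the study's objective as well as on safety. If a home record contains no skin finding, a reader may be unable to tell whether the skin was clear or nobody looked. A tabulation of skin effects could then look more favourable for home use because less was written down.

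**Working it through.** The documents give no figure to reproduce, so the check compares the passages directly.

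| Question | Lab | Home |
|---|---|---|
| Do staff observe the subject? | Yes (6.1.4) | Yes by 6.1.4; none described in 6.4.5 |
| Is the reaction recorded? | Required, in the CRF (6.4.4) | Optional, in the data collection device (6.4.5) |
| Are adverse events recorded? | Required (6.1.4, 14.3) | Required (6.1.4, 14.3) |
| Is the skin recorded at removal? | Not stated (6.4.4, 6.4.6) | Not stated (6.4.5, 6.4.6) |
| Who makes CRF entries? | Site staff (8.3) | Site staff (8.3) |
| How does a home entry reach the CRF? | Not applicable | Not stated |

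**Observation.** Section 6.1.4 is not limited to the lab, and its place under 6.1 General suggests that it covers both routes. In the virtual route, staff contact is described for phone screening (6.4.1.2) and for the health assessment and demographics call (6.4.3). Section 6.4.1.2 also says: "Virtual or In-person appointments are made once the phone screening process is completed." A virtual appointment could include live contact at placement, but no text extends it to overnight collection. The contradiction therefore stands.

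**Recording.** Sections 6.4.4 and 6.4.5 use almost the same sentence. They differ in *will* against *may*, and in the CRF against the data collection device.

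**From home to the forms.** A skin event at home must be noticed, written down or reported, read by site staff, and entered in the CRF and the Adverse Event Report Form. The protocol offers these partial routes:

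- Under 8.1, captured data are "shared with Masimo via a secure, password-protected server that only study staff and Masimo study team members will have access to." If this is the software named in 6.4.5, staff can reach home entries. Access is not a duty to read by a given time, and an optional entry may not exist.
- Under 6.3.5, parents complete other study documents and can be re-contacted by phone or email if these are deficient. The section does not say that the documents cover skin findings.
- Under 8.3 and 8.4, CRFs are completed on an ongoing basis, and missing or inconsistent data lead to queries. A query depends on something being seen as missing, and an optional item left blank need not be.

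None of these says who reads a home entry, by when, or how it reaches the two forms.

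**Size.** Section 7 targets a minimum of 25 subjects and 7.1 allows more, but the number studied at home is not given. Neither a skin event rate nor a share of events recorded is stated. A count of missed events would rest wholly on assumptions, so none is offered.

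**The case against.** The strongest reply is that adverse events are governed by their own mandatory text, with no home exception (6.1.4, 14.3). The optional sentence in 6.4.5 concerns placement, lot number, reaction and observations, and does not mention skin. This is right. A reader might infer that the plan lets skin adverse events go unrecorded at home, and the documents do not support that. What remains is how a home event becomes known and reaches the forms.

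Section 6.4.2 also requires a parent or guardian to be present for the whole study, and is worded for all subjects although it sits in the in-person section. This makes it likely that someone would notice a marked reaction. But a parent is not clinical study staff, and no duty on the parent to report skin findings is stated. For that reason the claim is confined to milder effects.

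The lab text is not complete either. Section 6.4.4 also makes observation for crying and restlessness optional and names no skin check at removal, and 6.4.6 is not specific to either setting. The gap at removal is therefore common to both settings, and the remedy should be too.

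A reader might see a conflict within 6.4.5, because its preceding paragraph says: "If applicable, the observations will be recorded in the data collection device." That sentence is conditional and follows the mention of crying and restlessness, while the next covers a wider list. Both can be followed together, so this is loose drafting. In 4.3, only the crash cart is clearly tied to the site; the instruction to call emergency services is not limited to the lab.

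Finally, the separate monitoring plan (6.5), the CRF, the procedure manual and the permission form may supply the missing steps. They were not available. They could close the recording gap, but would not by themselves remove the contradiction between 6.1.4 and 6.4.5.

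**Conclusion.** The point holds in a limited form and is worth an amendment. The contradiction between 6.1.4 and 6.4.5 is plain from the text. The consequence for the data is an inference: milder skin effects listed in 4.2 may be less completely recorded at home, because the reaction record is optional there and no transfer step is stated. It rests on the protocol text alone and on home sessions being run as 6.4.5 describes.

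Two further readings are not supported. A reader might infer that home events will miss the 14.3 limits; the documents state neither when those limits start nor how often home entries are read, so no breach is shown. A reader might also infer a much longer sensor exposure at home from the permitted length of home participation; actual wear time is not stated, so no exposure comparison can be made.

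**What to change.** 1. Reconcile 6.1.4 and the crash cart text in 4.3 with 6.4.5, so that the observation and emergency text matches what happens in a home session. No clinical rule is proposed here.
2. In 6.4.5, change *may* to *will* for recording the subject's reaction and observations.
3. In 6.4.6, add one required item at sensor removal for both settings: skin at the INVSENSOR00061 site, with the options finding present, finding absent, or not looked at. The parent reports it at home. This separates a clear site from an unexamined one and allows tabulation by setting.
4. State that site staff read home entries in time for the 14.3 limits and transfer them to the CRF and, for an adverse event, to the Adverse Event Report Form.

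The cost is a protocol amendment with IRB approval (Section 9), one data item, and a short reading and transfer task for site staff. No visit is added. A few more minor skin findings may be reported.
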